14.5 Physical Examination and Neurological Examination

A general physical examination, in addition to a neurological examination (cranial nerves, motor, sensory, reflexes, gait, and coordination), are performed at Screening and Week 8/ET visits.

Physical and neurological examination results (normal, abnormal, and not done) at Screening and Week 8 will be summarized descriptively by body/neurological system and visit.

14.6 Other Safety Variables

14.6.1 MMSE

The MMSE total score will be summarized by timepoint (Baseline, Week 4, and Week 8) using descriptive statistics. The change from Baseline scores will also be summarized descriptively at Week 4 and Week 8. In addition, the MMSE total score change from Baseline will be analyzed using an MMRM similar to the primary efficacy endpoint. The dependent variable will be the MMSE total score change from baseline, and the independent variables in the model will include the following: visit (Weeks 4 and 8), Baseline MMSE total score (continuous covariate), and Baseline MMSE total score-by-visit interaction.

The individual item scores will be listed but not summarized.

14.6.2 MDS-UPDRS Part III

The MDS-UPDRS Part III total score will be summarized by timepoint (Baseline, Week 4, and Week 8) using descriptive statistics. The MDS-UPDRS Part III total score change from Baseline will be summarized descriptively at Week 4 and Week 8, and will also be analyzed using an MMRM similar to the primary efficacy endpoint. The dependent variable will be the MDS-UPDRS Part III total score change from baseline, and the independent variables in the model will include the following: visit (Weeks 4 and 8), Baseline MDS-UPDRS Part III total score (continuous covariate), and Baseline MDS-UPDRS Part III total score-by-visit interaction.

The Hoehn and Yahr Stage will be summarized descriptively by visit as a categorical variable.

The individual item scores and all remaining questions will be listed but not summarized.

14.6.3 Suicidality

The C-SSRS is assessed at Screening, Baseline, Weeks 2, 4, 6, and Week 8/ET visits.

The event counts and the number and percentage of subjects in each suicide category at any post-Baseline timepoint (including unscheduled and out of window visits), will be summarized descriptively. Suicide categories will be defined as follows.

- Suicidality: Subjects who report at least one post-Baseline occurrence of suicidal behavior or suicidal ideation

- Suicidal ideation: Subjects who report at least one post-Baseline occurrence of the following
 - wish to be dead
 - non-specific active suicidal thoughts
 - active suicidal ideation with any methods (not plan) without intent to act
 - active suicidal ideation with some intent to act, without specific plan
 - active suicidal ideation with specific plan and intent
- Suicidal behavior: Subjects who report at least one post-Baseline occurrence of the following
 - Preparatory acts or behavior
 - Aborted attempt
 - Interrupted attempt
 - Actual attempt
 - Suicide

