	
 
13. Has a current diagnosis of delirium
 
14. Has a current primary diagnosis of borderline, antisocial, paranoid, schizoid, schizotypal, or histrionic personality disorder, according to DSM-5 criteria
 
15. Has met DSM-5 criteria for substance use disorders within the last 6 months prior to Screening, except for disorders related to the use of caffeine or nicotine
 
16. Has a positive test for an illicit drug at Screening or Baseline. Subjects who test positive for a controlled substance and who have a valid prescription can be enrolled if the drug is not a prohibited medication
 
17. Actively suicidal at Visit 1 (Screening) or Visit 2 (Baseline) (including an answer of “yes” to C-SSRS questions 4 or 5 [current or over the last 6 months]) or has attempted suicide in the 2 years prior to Visit 1 (Screening)
 
18. Is pregnant or breastfeeding. Female subjects of child-bearing potential must have a negative serum pregnancy test at Screening
 
19. Has major surgery planned during the trial (including Screening and follow-up periods)
 
20. Has participated in or is participating in a clinical trial of any investigational drug, device, or intervention, within 60 days (or five half-lives, whichever is longer) prior to Screening
 
21. Has previously been treated with pimavanserin or is currently taking pimavanserin
 
22. Has a sensitivity to pimavanserin or its excipients
 
23. Is judged by the Investigator or the Medical Monitor to be inappropriate for the study
 

Sample Size Calculations
	
The initial sample size calculation was based on a standard deviation of 8.0 and a dropout rate of 10%. An interim review of the statistical assumptions was conducted after 9 subjects completed the Week 8 visit, and the sample size was recalculated. The standard deviation in HAMD-17 total score change from Baseline to Week 8 was observed to be lower, and the dropout rate higher, than the initial assumptions. Therefore, the sample size has been recalculated as follows.
 
Assuming the standard deviation for the change in HAMD-17 total score from Baseline to Week 8 is 6.0 points, 34 evaluable subjects will provide 80% power to detect a minimum mean reduction of 3 points from Baseline to Week 8 at a significance level of 0.05 using a 2-sided paired t-test.

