
	
Baseline in HAMD-17 total score), the proportion of responders will be summarized by visit, including 95% confidence intervals. Observed cases (subjects with missing values at a given visit are excluded) as well as missing values imputed as non-responders will be presented.
 
Safety Analyses
 
Safety endpoints will be summarized using descriptive statistics. UPDRS Part III and MMSE will be analyzed using similar MMRM models as for the primary efficacy endpoint, except that the Baseline value of the endpoint being analyzed (either UPDRS Part III or MMSE) will be included as a covariate, and in the Baseline score-by-visit interaction term, instead of the HAMD-17 total score.
 
Adverse events will be classified into standard terminology using the Medical Dictionary for Regulatory Activities (MedDRA). Treatment-emergent adverse events (TEAEs), TEAEs leading to discontinuation, TEAEs related to study drug, TEAEs by maximum severity, serious adverse events (SAEs), and SAEs related to study drug will be summarized.
 
Descriptive statistics for ECG, vital signs and weight, C-SSRS, MMSE, UPDRS Part III, and clinical laboratory parameters, including changes from Baseline, will be tabulated by time point. Additionally, categorical analyses will be conducted on the incidence of subjects with prolonged QTc intervals and changes in QTc intervals in accordance with International Council for Harmonisation (ICH) guidelines.

Date	8 January 2019

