5.2.6 Columbia-Suicide Severity Rating Scale (C-SSRS)

The C-SSRS is assessed at Screening, Baseline, Weeks 2, 4, 6, and 8/ET visits.

The C-SSRS Baseline/Screening version will be completed at the Screening visit and the version assessing information since the last visit will be completed at Baseline, Week 2, Week 4, Week 6, and Week 8/ET.

The C-SSRS monitors changes in suicidal thinking and behavior over time in order to determine risk. Four constructs are measured: the severity of ideation, the intensity of ideation, behavior, and lethality.

There are 5 questions about suicidal ideation: wish to be dead; non-specific active suicidal thoughts; active suicidal ideation with any methods (not plan) without intent to act; active suicidal ideation with some intent to act, without specific plan; active suicidal ideation with specific plan and intent. If a subject answers "yes" to any of these 5 questions, this subject will be counted as having suicidal ideation.

There are 5 questions about suicidal behavior: suicide, actual attempt; interrupted attempt; aborted attempt; preparatory acts or behavior. If a subject answers "yes" to any of these 4 questions, this subject will be counted as having suicidal behavior.

Missing values will not be imputed.

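### The planned C-SSRS tables count any post-Baseline suicidal ideation or behavior without a by-visit or pre-treatment reference, so they do not separate new or worsened ideation from ideation carried into the study

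*SAP*

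**What the plan says.** **Protocol.** The C-SSRS is one of the safety endpoints (Section 2.3.1). The Safety Analyses paragraph of the synopsis groups it with other measures and says that "C-SSRS, MMSE, UPDRS Part III, and clinical laboratory parameters, including changes from Baseline, will be tabulated by time point". Exclusion 17 covers subjects who are actively suicidal at Screening or Baseline. The C-SSRS answers that it names are a positive response to "C-SSRS questions 4 or 5 [current or over the last 6 months"; it also excludes a suicide attempt in the two years before Screening.

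**SAP.** Section 5.2.6 states that "The C-SSRS Baseline/Screening version will be completed at the Screening visit", with the since-last-visit form used at Baseline and afterwards. It adds that, after a positive answer to "any of these 5 questions, this subject will be counted as having suicidal ideation". Section 14.6.3 says that event counts and numbers of subjects in each suicide category "at any post-Baseline timepoint (including unscheduled and out of window visits), will be summarized descriptively". Suicidality is defined there as "Subjects who report at least one post-Baseline occurrence of suicidal behavior or suicidal ideation". The ideation and behavior categories follow the same any-occurrence pattern. Section 18 answers that changes to the protocol's analyses are not applicable.

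**The concern.** The study has one arm, so each subject's own pre-treatment status is the only reference within the study for judging suicidality on drug. Section 14.6.3 does not use it. A subject who had passive ideation before the first dose and still has it at Week 2 falls in the same category as a subject whose ideation began on treatment. A subject who moves from question 3 to question 1 is also counted as having suicidal ideation. One who moves from question 1 to question 3 stays in the pooled category, and the worsening does not show.

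At stake is whether the summary tables can answer the obvious safety question in a depressed population: did ideation appear or worsen after treatment started? There is also a consistency issue, because the synopsis commits to a by-visit, Baseline-referenced tabulation that Section 14.6.3 does not specify and Section 18 does not mention.

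**Working it through.** **1. Commitment against plan.**

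| Feature | Protocol synopsis | SAP 14.6.3 |
|---|---|---|
| By time point | Yes | No; one pooled post-Baseline period |
| Change from Baseline | Yes | No |
| New or worsened category | Not specified | No |

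**2. Is this the SAP's general approach?** No. MMSE and MDS-UPDRS Part III (14.6.1, 14.6.2) have by-visit and change-from-Baseline summaries. Laboratory values (14.2) and ECG interpretation (14.4) have shift tables, including shifts to the post-Baseline extremes or worst result.

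**3. Can carried-over ideation reach the table?** The exclusion names questions 4 and 5. The SAP's ideation definition uses questions 1 to 5. Questions 1 to 3 therefore count as an outcome without being named as a bar to entry.

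**4. Is the pre-treatment status shown elsewhere?** SAP 8.2 summarises ideation or behavior ever, and within the past 6 months, each as yes or no. These are group totals and are not crossed with post-Baseline outcome.

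**5. Denominator.** The documents give no figure for suicidality. They plan about 40 subjects: 34 evaluable with up to 15% non-evaluable, and 34 / 0.85 = 40. The 34 also reproduces: a two-sided paired t-test with difference 3, SD 6.0 and alpha 0.05 has power 0.808 at n = 34. Nothing here disputes that calculation.

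**6. Illustration, on assumed rates.** Let b be the share with ideation at entry, q the share of those who report it again after Baseline, and e the rate of new ideation in the rest. Then

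planned count = 40 × b × q + 40 × (1 − b) × e,

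and only the second term is emergent.

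| b | q | e | Carried over | Emergent | Planned count |
|---|---|---|---|---|---|
| 10% | 50% | 0 | 2.0 | 0 | 2.0 (5%) |
| 40% | 80% | 0 | 12.8 | 0 | 12.8 (32%) |
| 10% | 50% | 5% | 2.0 | 1.8 | 3.8 (9.5%) |
| 40% | 80% | 5% | 12.8 | 1.2 | 14.0 (35%) |
| 40% | 50% | 0 | 8.0 | 0 | 8.0 (20%) |
| 20% | 80% | 5% | 6.4 | 1.6 | 8.0 (20%) |

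The last two rows give the same planned count of 8. In one no case is emergent; in the other between one and two are.

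**The case against.** **The information is not lost.** A reader might infer that emergent suicidality cannot be separated from prior ideation in this trial. The documents do not support that. SAP Section 5 says all collected data will be listed, and with about 40 subjects pre- and post-treatment records can be matched by hand. Suicidality recorded as an adverse event also passes through the treatment-emergent definition in Section 14.1. This stands and limits the point to the planned tables. It does not remove it: hand-matching is not a prespecified summary, and the adverse event route depends on the investigator recording the C-SSRS response as an event.

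**The most serious levels are largely covered.** Ideation at questions 4 or 5 in the 6 months before entry, and attempts in the previous two years, are excluded. A later occurrence is therefore new relative to those windows. Section 14.6.3 also itemises the five ideation and five behavior levels, and the table shells, held in separate documents, may give each its own row. Post-Baseline forms ask only about the time since the last visit. All this stands, and it is why the point mainly concerns ideation at questions 1 to 3. Separate rows would show the level reached, but not the level it started from.

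**Entry with lower-level ideation is not assured.** Exclusion 17 concerns active suicidality and includes, without being limited to, questions 4 and 5; exclusion 23 leaves further discretion. The documents permit such entry but do not say how often it happens.

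**The protocol text is incomplete here.** Section 9.9.7, on suicidal ideation and behavior, is in the table of contents but not in the text available for review. The commitment therefore rests on one synopsis sentence covering several measures, most of them numeric. The SAP describes no C-SSRS total score, so a change from Baseline has no set meaning for it. One should not infer that the protocol's detailed section has been contradicted. SAP 5.3 also says in general terms that safety assessments are summarised by analysis visit, but it defines windows and does not specify a C-SSRS table.

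**The direction of error is mild.** An any-occurrence count drops no case. It overstates on-treatment onset; a new case can go unrecognised among carried-over ones, but it is still counted.

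**Conclusion.** The point holds for the planned summary tables. The synopsis commits to a by-visit, Baseline-referenced C-SSRS tabulation, Section 14.6.3 specifies neither feature, and Section 18 declares no departure. As planned, the tables treat persisting, improving and new ideation at questions 1 to 3 alike, and the pooled ideation category does not show worsening.

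The size is unknown, because the documents give neither entry prevalence nor persistence. On assumed rates of 10–40% at entry and 50–80% persistence, about 2 to 13 of 40 subjects would be flagged with none emergent. Larger figures are tempting, since full persistence at 20–40% prevalence would give 8 to 16 (0.20 × 40 and 0.40 × 40), but nothing in the documents supports assuming that every case persists.

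The primary analysis, alpha, power and sample size are unaffected. This is a reporting gap on one safety endpoint. It is worth closing because the remedy is cheap and follows the approach the SAP already takes for laboratory values and ECG interpretation.

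**What to change.** In SAP Section 14.6.3:

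- Add the by-visit C-SSRS summary to which the synopsis commits.
- Add a shift table from worst pre-treatment category to worst post-Baseline category, with ordered ideation levels and behavior shown separately.
- Add counts of subjects with new or worsened ideation or behavior, defined as a post-Baseline category worse than the pre-treatment reference.
- State the pre-treatment reference as a recent recall window: for example, the 6-month period at Screening that Section 8.2 already summarises, plus the Baseline since-last-visit form. Lifetime history should not enter it, or a recurrence on drug could be classed as not emergent. The general rule in Section 5.3 (last non-missing result before dosing) does not suffice, because it would normally select the Baseline form and ignore the Screening form.

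If the sponsor prefers the present tables, Section 18 should declare and justify the departure from the synopsis.

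The cost is one or two extra tables. Screening and Baseline C-SSRS data are already collected. The shift table assumes that answers are held question by question for the chosen window, which Exclusion 17 and Section 8.2 suggest but do not state.

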15 CLINICAL PHARMACOKINETIC AND PHARMACODYNAMIC ANALYSES

Not applicable

16 DATA MONITORING/REVIEW COMMITTEE

Not applicable.

17 COMPUTER METHODS

Statistical analyses will be performed using Version 9.4 (or newer) of SAS software (SAS Institute Inc., Cary, NC, USA) on a suitably qualified and validated environment.

Validation and quality control of the tables, listings, and figures containing the results of the statistical analyses will follow appropriate standard operating procedures.

18 CHANGES TO ANALYSES SPECIFIED IN PROTOCOL

Not applicable.

19 APPENDICES

19.1 Summary of Version Changes

Version No:	Document History Description of Update	Author(s)	Version Date
1.0	Original version	[REDACTED]	12 September 2018
2.0	Revised Section 3.5 due to sample size reduction per Protocol Amendment 2; and made update to Section 13.1.2 to use paired t-test (instead of ANCOVA) as per protocol. Updated primary objective to agree with Protocol Amendment 2 (adjunctive treatment no longer restricted to SSRI/SNRI). Updated Section 12.1.2 to agree with Protocol Amendment 2 (ANCOVA changed to t-test).	[REDACTED]	31 January 2019
